**14.1.1. Primary Analysis**

The cORR will be provided with a corresponding Clopper-Pearson (exact) binomial 95% CI (Clopper CJ et al, 1934) for the ES. The two-stage method will be used to test the null hypothesis with the possibility of stopping accrual earlier for futility. If the observed cORR at the end of the first stage is less than 28% (i.e.,  $\leq 11$  confirmed CRs + PRs among 40 treated subjects with a centrally confirmed *BRAF*V600E mutation), then insufficient efficacy will be concluded. Otherwise, at the end of stage 2, if the observed cORR is  $\geq 41\%$  (i.e.,  $\geq 37$  confirmed responses among 90 treated subjects with a centrally confirmed *BRAF*V600E mutation), the null hypothesis will be rejected.

In case of  $N > 90$  subjects treated with a centrally confirmed *BRAF*V600E mutation, this analysis will be repeated for the Stage 2 analysis, when excluding the overrunning subjects (i.e. on the 90 first treated subjects with a centrally confirmed *BRAF*V600E mutation).

In addition to the Stage 1 and Stage 2 analyses, the analyses for cORR will also be conducted at the time of the end of study.

### 14.1.2. Supportive Analyses

The cORR will be provided with a corresponding Clopper-Pearson (exact) binomial 95% CI for the PPS and FAS (see section 7).

In order to assess the impact of the Urgent Safety Measure (USM) implemented during the COVID-19 pandemic (see section 15.1), the cORR will be provided with a corresponding Clopper-Pearson (exact) binomial 95% CI, on the subset of the ES composed of subjects who benefited from the USM.

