6.5.4. Dose Modification

Subjects will be monitored for AEs. The severity of AEs will be evaluated using the NCI-CTCAE v.4.03.

If a subject develops toxicity, the dose should be modified as outlined in **Table 14** and **Table 15**, which include criteria for interruption and reduction of encorafenib, binimetinib and cetuximab. All dose modifications should be based on the worst preceding toxicity. All dosing interruptions and modifications must be recorded in the e-CRF.

If a subject permanently discontinues binimetinib due to an AE or clinically significant laboratory value, they may continue to receive encorafenib in combination with cetuximab.

Due to the lack of efficacy of binimetinib, encorafenib, or cetuximab when used as single agents in subjects with *BRAF*-mutant mCRC, subjects who cannot tolerate these agents in combination with at least one other agent, should discontinue study treatment altogether, complete the end of treatment visit and continue to be followed for survival (and disease progression, if applicable).

Cetuximab may be reduced by 2 dose levels to a minimum of 150 mg/m², due to AEs or laboratory abnormalities (**Table 8**). When a dose reduction is required because of an AE, no subsequent dose re-escalation of cetuximab will be permitted for that subject for the duration of study treatment. If after resolution of an AE, treatment is resumed at the same dose, and the same toxicity reoccurs with the same severity, any re-initiation of treatment must be at the next lower dose level irrespective of duration, with some exceptions for skin toxicity.

In addition, a subject must discontinue study treatment if, after treatment is resumed at a lower dose of cetuximab, the same toxicity reoccurs with the same or worse severity.

If a subject misses > 28 consecutive days of encorafenib or binimetinib, or > 4 consecutive cetuximab doses as the result of an AE or clinically significant laboratory abnormality, then the respective agent(s) should be discontinued.

Subjects who discontinue study treatment for a study-related AE or an abnormal laboratory value must complete the end of treatment visit and continue to be followed for survival (and disease progression).

Table 8: Dose Levels for Dose Modification

	Encorafenib (mg QD)	Binimetinib (mg BID)	Cetuximab WEEKLY (mg/m²)	Cetuximab BI-WEEKLY (mg/m²) Starting from C8D1 week 29 Or at any cycle since implementation of the Urgent Safety Measure on 26 Mar 2020

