### 15.1. TREATMENT EXPOSURE

Duration of study drug exposure to any dose (in weeks), actual and relative dose intensity will be summarized.

The number of subjects with at least one dose reduction will be presented, along with reasons for the dose reduction. The same table will be provided for dose interruptions, and for dose reductions or interruptions. The number of subjects with at least one definitive dose reduction (i.e. subjects with a dose reduction and who did not re-escalate to the protocol-planned dose) will be described. The actual daily doses and reasons for dose reductions/interruptions will be listed in an individual basis for subjects with dose reductions/interruptions.

A dose interruption will be indicated in the eCRF by a dosing record with a total daily dose of 0 mg for one or more days.

To avoid over-counting interruptions, dosing records with 0 mg entered as last dosing record will not be counted as interruptions (those represent the reason for permanent discontinuation and will therefore be presented in the reason for treatment discontinuation analysis).

A dose reduction is defined as a decrease in dose from the protocol-planned dose and a decrease from the previous non-zero dose, even if this decrease has been directly preceded by an interruption. For example, for encorafenib, in the sequence of total daily dose 300 mg – 0 mg – 200 mg, the 200 mg dose will be counted as a reduction.

These analyses will apply for each study drug (encorafenib, binimetinib and cetuximab) individually on the FAS.

- **Duration of study drug exposure** (weeks)

This is the duration that the patient was exposed to the study drug and is defined as  $([\text{Date of last (non-zero) dose of study drug}] - [\text{date of first dose of study drug}] + [\text{days until next dose}]) / 7$ .

For encorafenib/binimetinib, [days until next dose] = 1.

For Cetuximab,

- before switch to a biweekly infusion: [days until next dose] = 7
- from switch to a biweekly infusion: [days until next dose] = 14

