NB: In the initial version of the study protocol, patients were planned to switch to cetuximab infusions at dosage of 500 mg/m^2 administered every 2 weeks (i.e. D1 and D15) at C8D1, instead of weekly infusions at dosage of 250 mg/m^2 (except first administration with dosage of 400 mg/m^2). Following the COVID-19 pandemic outbreak, an Urgent Safety Measure (USM) was implemented to allow the investigators to perform Cetuximab infusions at dosage of 500 mg/m^2 administered every 2 weeks (i.e. D1 and D15) instead of weekly, whatever the cycle (even if the subject has not reached yet C8D1), after having evaluated the benefit/risk for the subject and in order to reduce the number of visit at hospital.

For subjects who benefited from this USM, records post-decision to switch to an administration every 2 weeks will be derived as follows:

- 1) First step: Among the subjects having received at least one dose of study treatment (complete or partial): only the subjects who didn't have their C8D1 before the 01MAR2020 and who didn't discontinue treatment before 01MAR2020 and who didn't discontinue cetuximab before 01MAR2020 are to be considered
- 2) Among the subjects selected from first step, subjects with an administrated dose > 400 mg/m^2 before C8D1 will be considered as having benefited from the USM.
- 3) This subset of subjects will be cross-checked with reason mentioned for dose modification.  
Dose modifications for reasons not related to COVID-19 pandemic will be excluded

The date of switch to a biweekly infusion for a given subject will be derived as the first date among selected records for this subject.

NB: any infusion after this date at dosage < 500 mg/m^2 will be considered as a dose reduction, even if occurring before C8D1.

Duration of study drug exposure will also be described as a discrete variable, with modalities t to < t+4 weeks (t being the duration of exposure, in weeks), such as: < 4 weeks / 4 - < 8 weeks / 8 - < 12 weeks / etc.

▪ **Relative dose intensity (RDI) (%)**

- **Cumulative actual dose (mg or mg/m^2)** is the total dose given during the study treatment exposure. The cumulative actual dose for a given patient is the sum of the actual dose received (mg or mg/m^2). The actual dose received for Cetuximab (mg/m^2) at cycle i is equal to the actual dose received (mg) at cycle i divided by the body surface area at the beginning of cycle i

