  - NB: If needed, the BSA at a given timepoint will be derived according to formula displayed in section **Erreur ! Source du renvoi introuvable.** (with same rounding convention)

For encorafenib and binimetinib (daily dosing):

- Duration of planned exposure (this is not summarized in any exposure table) = [Date of EOT or data cut-off (the earliest one)] – [date of first dose of study drug] + 1
- Dose intensity (mg/day) = [Cumulative actual dose]/[duration of planned exposure]
- Cumulative planned dose (mg) = sum(protocol specified dose across each day of planned exposure)
- Planned dose intensity (mg/day) = [Cumulative planned dose]/[duration of planned exposure].  
For encorafenib, PDI = 300 mg/day. For binimetinib, PDI = 90 mg/day.
- Relative dose intensity (%) = 100 x [Dose intensity]/[Planned dose intensity]

For Cetuximab (intermittent dosing):

- Duration of planned exposure (this is not summarized in any exposure table) = [Date of EOT or data cut-off (the earliest one)] – [date of first dose of study drug] + 1
- Duration of planned exposure after switch to a biweekly infusion (this is not summarized in any exposure table) = [Date of EOT or data cut-off (the earliest one)] – [date of first dose of study drug] - [number of days with weekly infusion] + 1

- planned day of the first visit when switch occurred is the theoretical day (based on C1D1) of the first visit where the subject was under weekly regimen. It represents the duration subject was under weekly regimen.
  - For instance, for subjects who did not benefit from the USM and switched to biweekly infusions starting from C8D1, as initially planned in the protocol: planned day of the first visit when switch occurred = 197, meaning 196 (28\*7) planned days under weekly regimen.
  - For subjects who benefited from the USM, number of days with weekly infusion can be derived using the visit of switch to a biweekly infusion (as derived above) and the theoretical day of visits
- This is calculated only if date of EOT or data cut-off (the earliest one) is after the switch to a biweekly infusion (28 weeks in the initial protocol (i.e. Duration of planned exposure > 196 (28\*7) days) or USM)

Let xx be the planned day of the first visit under biweekly regimen (197 in the initial protocol, where dosed bi-weekly from week 29/C8D1 or planned day of the first visit when switch occurred for subjects with USM):

- o Number of planned doses = number of non-zero doses plus the number of interrupted doses.

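### Minor: the SAP 15.1 flag (cetuximab dose above 400 mg/m²) misses Urgent Safety Measure switchers who were already dose-reduced, and the SAP 14.1.2 subset cORR is descriptive, not a measure of impact

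*SAP*

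**What the plan says.** **Dosing.** Since 26 Mar 2020, Protocol 6.5.3 lets cetuximab be given every two weeks at 500 mg/m² at any cycle, ahead of the scheduled change at C8D1. If the dose was modified before the change, the total per cycle is kept; the example is 200 weekly becoming 400 every two weeks. SAP 6.1 repeats this. Table 8 in Protocol 6.5.4 lists biweekly levels of 500, 400 and 300, valid from C8D1 "Or at any cycle since implementation of the Urgent Safety Measure on 26 Mar 2020". The same section does not allow cetuximab to be raised again after a reduction for an adverse event.

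**Who counts as a USM switcher (SAP 15.1).**
- Step 1: only subjects who had not reached C8D1 or stopped treatment before that date, and who did not "discontinue cetuximab before 01MAR2020 are to be considered".
- Step 2: "subjects with an administrated dose > 400 mg/m 2 before C8D1 will be considered as having benefited from the USM".
- Step 3: dose modifications with a reason unrelated to COVID-19 are removed.
- "The date of switch to a biweekly infusion for a given subject will be derived as the first date among selected records". A note adds that any later infusion below 500 counts as a dose reduction, even before C8D1.

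**Reductions (SAP 15.1).** "A dose reduction is defined as a decrease in dose from the protocol-planned dose and a decrease from the previous non-zero dose". A definitive reduction covers "subjects with a dose reduction and who did not re-escalate to the protocol-planned dose".

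**Use (SAP 14.1.2).** The cORR and its exact interval are given on the "subset of the ES composed of subjects who benefited from the USM". The stated purpose is to assess the USM's impact, and no comparator is named. SAP 8 and SAP 20 class the analysis as exploratory.

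**The concern.** There are two linked problems.

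First, the flag sees one of the three biweekly levels in Table 8. A subject already at 200 or 150 weekly switches to 400 or 300, and neither exceeds 400. After a reduction for an adverse event the dose cannot rise later, and step 3 only removes subjects. The subject leaves the 14.1.2 subset, has no USM switch date, and is handled as weekly until C8D1 in the cetuximab exposure derivation.

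Second, membership depends on time on treatment. Subjects who left before 01MAR2020 cannot enter, and responses already confirmed on weekly dosing count in full. A subset cORR above the Efficacy Set (ES) cORR could then arise with no USM effect at all, while the stated purpose invites reading it as one.

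**Working it through.** **The plan's own figures.** The documents give no figure for the USM subset. The design figures reproduce: the exact two-stage binomial (stop at 11 or fewer of 40; reject at 37 or more of 90) gives one-sided alpha 0.0161 at 30% and power 0.798 at 45%, against the stated 1.6% and 80%. The exact interval for 37/90 is 30.8% to 52.0%, as stated. Nothing below touches them.

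**The flag against Table 8 (nominal doses, mg/m²).**
- 250 weekly to 500: above 400, flagged.
- 200 weekly to 400: not above 400, missed.
- 150 weekly to 300: missed.

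The strict cut has a reason: the C1D1 dose is 400, so a cut at 400 or more would flag nearly everyone. It is also fragile. With body surface area (BSA) rounded to one decimal, a nominal 400 becomes 400 × 1.64/1.6 = 410 or 400 × 1.66/1.7 = 390.6. Step 2 sets no earliest date for the infusion, so a C1D1 dose could pass it by chance.

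**How many could be missed.** C8D1 is first dose + 196 days. A USM switch before C8D1 needs C8D1 after 26 Mar 2020, so a start after 12 Sep 2019. The last start was 27 Dec 2019 (Protocol synopsis). Assume even accrual of 90 subjects from 1 Nov 2018:
- Starts from 13 Sep to 27 Dec 2019: 106 of 422 days; 106/422 × 90 = 22.6, about 23.
- If 3% to 10% were reduced before switching (assumed): 22.6 × 0.03 = 0.7 to 22.6 × 0.10 = 2.3, so about 1 to 2, before allowing for those who left or did not switch.

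A small number is consistent with one grade 3/4 skin event in 30 patients in the earlier triplet safety lead-in (Protocol 1.2.3), but the documents give no reduction rate.

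**Exposure for a missed subject (assumed history).** 400 on day 1, 250 weekly on days 8-50, 200 weekly on days 57-92, then 400 every two weeks on days 99-169, with end of treatment on day 180, before C8D1 (day 197).
- Duration: (169 − 1 + 7)/7 = 25 weeks unflagged; (169 − 1 + 14)/7 = 26 weeks flagged.
- Dose given: 400 + 7×250 + 6×200 + 6×400 = 5750.
- Dose planned: unflagged 400 + 25×250 = 6650; flagged 400 + 13×250 + 6×500 = 6650. Relative dose intensity is 5750/6650 = 86.5% either way.
- With end of treatment on day 175, the unflagged plan is 400 + 24×250 = 6400, so 89.8% against 86.5%.

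**Reduction tables.** If the planned dose stays 250 for an unflagged subject (SAP 15.1 does not say so outright), 400 after 200 reads as a return to plan, and a later step from 400 to 300 is not below plan.

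**Time on treatment and timing of response.**
- 27 Dec 2019 to 01 Mar 2020 is 65 days, the minimum time since first dose for any member.
- Scans fall at week 6 (day 49 at the latest) and week 12 (day 77 at the earliest). 77 − 49 = 28 days, so the pair can meet the four-week confirmation rule in SAP 14.1.
- A late in-window week-12 scan is at start + 84 + 7 = 91 days. For starts up to 25 Dec 2019 this falls before 26 Mar 2020.

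**Possible size of selection (assumed inputs).** With ES cORR 45%, 20% leaving before the switch and response rate r among leavers, the subset cORR is (0.45 − 0.20r)/0.80. This is 45% at r = 0.45, 51% at r = 0.20 and 56% at r = 0.

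**Precision (assumed).** 9 responders of 20 gives an exact 95% interval of 23% to 69%.

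**The case against.** The case on the other side is substantial.

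- *The analysis is already exploratory.* SAP 8 reserves causal interpretation for the primary test, SAP 20 labels this analysis exploratory, and 14.1.2 tests nothing. This stands. Only the stated purpose, repeated in SAP 20, and the lack of a before/after split are left.
- *Reductions are still counted.* A reader might infer that the dose-reduction tables are wrong throughout. They are not. Every missed subject was already reduced and so appears under at least one dose reduction. Adverse events leading to reduction are tabulated from the action-taken field (SAP 15.2), independently of the flag. At most, the definitive-reduction line or the reason for a second step could change, and that depends on an inferred planned dose.
- *Few subjects are affected.* This is probably true. But the contradiction between step 2 and Table 8 does not depend on the count.
- *A looser cut would be worse.* Lowering the threshold to 400 would catch the C1D1 dose. This is right, and the repair should use date and change in dose rather than a lower fixed cut.

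**Conclusion.** The rule is wrong as written, and the point is minor. At nominal doses the flag misclassifies any subject reduced before a USM switch; this follows from the text without assumptions. Its reach is limited to membership of the 14.1.2 subset, a 7-day rather than 14-day exposure tail if cetuximab stops before C8D1, and possibly the definitive-reduction line or the reason for a second reduction. Relative dose intensity changes little: not at all in the day-180 example, and 3.3 points for one subject in the day-175 example. About 1 to 2 subjects missed rests on assumed even accrual and an assumed 3-10% reduction rate; it is not a bound. The primary analysis is unaffected.

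The subset cORR is descriptive and selected on time on treatment. A reader might go further and conclude that it is biased upwards by a known amount, or that the SAP will claim a USM effect. The documents support neither. The excess is zero if leavers respond as often as those who stay, no departure rates are given, and SAP 8 rules out a causal claim.

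**What to change.** 1. **SAP 15.1, step 2.** Reconcile the flag with Table 8. Among infusions on or after the USM date and before C8D1 (which leaves out the C1D1 dose), flag the first whose dose rises above the subject's own preceding weekly dose by more than BSA rounding can explain and whose next infusion, if any, is about 14 days later. Take the switch date from that record. Weekly subjects who merely missed D8 or D22 show no rise, because omitted doses are not made up (Protocol 6.5.3). Avoid a fixed multiple such as 1.5. A step down at the switch gives 400/250 = 1.6 or 300/200 = 1.5; if rounding can take a doubling down to 1.86, a factor of 0.93, these fall to 1.49 and 1.40.
2. **SAP 15.1, step 3.** Keep it as an exclusion of non-COVID reasons only, so that a blank reason does not drop a true switcher.
3. **SAP 15.1, reductions.** Reconcile the note that counts any dose below 500 after the switch as a reduction with the definition that also requires a fall from the previous non-zero dose. For a reduced level carried over at the switch (200 weekly to 400 every two weeks) the two disagree.
4. **SAP 14.1.2.** Replace the impact purpose with a statement that the subset cORR is descriptive and selected on time on treatment. Report how many responses were confirmed before and after the switch date.

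Cost: SAP wording and a small derivation from infusion doses, dates and reasons, which the existing steps already use. It needs no new data and leaves the primary analysis unchanged.

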### 14.1.3. Exploratory Analyses

Primary analysis of the main criterion will be conducted for ES on the subgroups of subjects defined as:

- Age < 65 and  $\geq$  65 years old
- Males and Females
- Baseline CRP level ( $\leq$  local ULN and  $>$ local ULN)
- Baseline CEA ( $\leq$  local ULN and  $>$ local ULN)
- Baseline CA19-9 ( $\leq$  local ULN and  $>$ local ULN)
- MSI status at screening (MSI-High and Non MSI-High)
- Primary tumor location (right-sided and left-sided)

*Note:* Primary tumor location reported as “COLON, TRANSVERSE” will be considered as right-sided. Primary tumor location “Rectum” (reported as “Other”) will be considered as left-sided.

Patients with primary tumor location reported as “OTHER” (except “Rectum”, cf. above, and modalities considered as right-sided or left-sided cf. section 13) will not be included in this subgroup analysis.

- Number of metastatic organs (1, 2 and  $>2$ )

*Note:* “1”, “2-3” and “ $>3$ ” could be used if relevant (i.e. over-represented category)

- Baseline ECOG PS (0 and 1)

---

 Blood sample for MSI testing (control sample) will not be processed on an ongoing basis during the study, but once for all subjects enrolled. MSI Status will thus remain undetermined during the study and will be described when available (cf. [Appendix 5](#)).

The primary endpoint and the corresponding 95% CI will be displayed using a forest plot by subgroups.

At the time of the primary analysis (i.e. Stage 2 or at Stage 1 if study stops for futility), analysis of cORR based on investigator-assessed tumor evaluation will be repeated on the ES, when excluding the patients with no confirmed metastatic disease at inclusion (i.e. Inclusion criterion #3 not filled).

cORR based on investigator-assessed tumor evaluation for the subgroup of subjects in Japan will also be examined separately at the time of the primary analysis (i.e. Stage 2 or at Stage 1 if study stops for futility) on the ES and FAS, and according to MSI status at screening on the ES.

## **14.2. SECONDARY EFFICACY ENDPOINTS**

The statistical analyses for the secondary criteria will be described on the FAS unless otherwise stated.

### **14.2.1. cORR assessed by central radiologist review**

For each tumor assessment performed, central radiologist review is performed by two independent readers (“reader 01” and “reader 02”). When there is a discrepancy between both reviews, a third independent reader (named the “adjudicator”) will adjudicate and select one of the two readers.

The data sent by the external vendor include:

- Review of reader 01 and reader 02
- Adjudication, if any (“Agree with reader xx”).
  - NB: The adjudicator’s choice applies to all tumor assessments performed prior to the adjudication.
  - NB2: At any tumor assessment where an adjudication is performed for a given subject (until the last tumor assessment for this subject), the adjudicator’s choice may change, and this will apply to all tumor assessments performed prior to the last adjudication. This

means that for a given subject, the results as per central review may change, until the last tumor assessment reviewed, for this subject.

- 1) For each subject and each tumor assessment, only one reader will be used for statistical analysis. For a given analysis and a given subject: If no adjudication performed:
  - a. For tumor assessments where both readers are in agreement => Reader 01's assessment will be taken into account for analysis
  - b. For tumor assessments where both readers disagree => Tumor assessments will not be taken into account for analysis.
- 2) If at least one adjudication performed:
  - a. For all tumor assessments done until the last adjudication performed => Reader xx's assessment (according to the last adjudicator's choice) will be taken into account for analysis.
  - b. For tumor assessments done after the last adjudication performed:
    - i. For tumor assessments where both readers are in agreement => Reader xx's assessment (according to the last adjudicator's choice) will be taken into account for analysis.
    - ii. For tumor assessments where both readers disagree => Tumor assessments will not be taken into account for analysis.

The BOCR assessed by central imaging review will be derived as done for BOCR assessed by local review (see section 14.1).

The cORR assessed by central radiologist review will be provided with a corresponding Clopper-Pearson (exact) binomial 95% CI for the ES and FAS.

The cORR assessed by central radiologist review for the subgroup of subjects in Japan will also be examined separately at the time of the primary analysis (i.e. Stage 2 or at Stage 1 if study stops for futility).

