All imaging data acquired for efficacy purposes during the Main study period will be transmitted to an imaging vendor for central review. Image transmission to the imaging vendor should be accomplished according to the imaging vendor manual. Full details of the central reading process are included in the Independent Review Charter.

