**Table 12: Censoring rules for PFS**

In the below table, “new antineoplastic therapy” refers to any additional secondary antineoplastic medication or anti-cancer surgery or radiotherapy.

	Situation	Event Date	Outcome
No baseline tumor assessments			
A1	No baseline assessment and death after the second scheduled post-baseline tumor assessment, or no death	Date of first study treatment administration	Censored
A2	No baseline assessment and death on or before the second scheduled post-baseline tumor assessment	Date of death	Event
No post-baseline tumor assessments (without new antineoplastic therapy given)			
B1	Death on or before the second scheduled post-baseline tumor assessment	Date of death	Event
B2	Death after the second scheduled post-baseline tumor assessment or no death	Date of first study treatment administration	Censored
With baseline and post-baseline tumor assessments (without new antineoplastic therapy given prior progression or death without progression observed)			
C1	Progression with zero or one missed/inadequate tumor assessment prior to progression	Date of progression	Event
C2	Death but no progression, with zero or one missed/inadequate tumor assessment prior to death	Date of death	Event
D1	Progression but two or more consecutively missed/inadequate tumor assessments prior to progression	Date of last adequate tumor assessment*	Censored
D2	Death without progression, but two or more consecutively missed/inadequate tumor assessments prior to death	Date of last adequate tumor assessment*	Censored
E	No progression, no death	Date of last adequate tumor assessment*	Censored
F	Treatment discontinuation due to ‘Disease progression’ without documented progression, i.e. clinical progression based on investigator claim	N/A (not considered as an event, patient without documented PD should be followed for progression after discontinuation of treatment)	Information ignored
Initiation of new antineoplastic therapy given prior progression or death without progression observed			
G	New antineoplastic therapy started before progression or death	Date of last adequate tumor assessment prior to initiation of new antineoplastic therapy*	Censored
H	No post-baseline tumor assessment and new antineoplastic therapy started prior to a death	Date of first study treatment administration	Censored

\* tumor assessment with non-missing and non-unknown overall lesion response, as defined in section 9.3.

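### Central review: SAP 14.2.1 drops a discordant scan that has no adjudication at or after it, which can delay or censor central PFS and DOR events and move central cORR either way

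*SAP*

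**What the plan says.** SAP 14.2.1 starts from a plain principle: "When there is a discrepancy between both reviews, a third independent reader" is brought in, who "will adjudicate and select one of the two readers". That "choice applies to all tumor assessments performed prior to the adjudication", and it may change at a later adjudication for the same subject.

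The data-handling rules follow:

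- **Rule 2a**, "For all tumor assessments done until the last adjudication performed": the selected reader's readings are used, so discordant scans in that span are kept.
- **Rule 2b-i**, later scans on which the readers agree: the last selected reader is used.
- **Rules 1b and 2b-ii**, discordant scans in subjects with no adjudication, or after the last adjudication: "Tumor assessments will not be taken into account for analysis".

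Neither document says when a discrepancy triggers adjudication, how soon it is done, or what counts as disagreement. Protocol 8.1 defers this: "Full details of the central reading process are included in the Independent Review Charter".

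The rule reaches beyond response. SAP 14.2.3 refers back to 14.2.1 for handling central data. SAP 14.2.5 (PFS), 14.2.8 (DOR) and 14.2.10 (TTR) do not, but 14.2.1 speaks of the reader used for statistical analysis in general. For PFS, Table 12 row D1 adds a second step: "Progression but two or more consecutively missed/inadequate tumor assessments prior to progression" leads to censoring at the last adequate scan, judged by the distance limits in SAP 9.3 and Table 8.

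**The concern.** A scan dropped under 1b or 2b-ii is not missing: two readings of it exist. It is left out because they differ, so the omission is tied to the outcome being measured. If one reader called progression, the end event for PFS or DOR can be delayed or lost. If one reader called response, a confirmation can be lost. The gap left behind can also trip the two-missed-scans rule for a later progression on which both readers agree.

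In an open-label, single-arm trial with an investigator-assessed primary endpoint, the central results are the independent view of the same scans. The SAP plans no count of dropped scans and no analysis by reader, so a reader of the report could not judge the effect.

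**Working it through.** **Distance limit.** SAP 9.3 gives an 8-week interval with windows of 7 days. For a last adequate scan on study day 64 or later, D2 = 2×8×7 + 7 + 7 = 126 days, as Table 8 states. Planned scans fall on days 42 and 84, then every 56 days: 140, 196, 252.

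**Example 1, PFS.** Both readers give SD on day 84. On day 140 one gives PD and the other SD, with no adjudication and no later scan. The day-140 scan is dropped and PFS is censored at day 84 (Table 12 row E). With adjudication, the result is an event at day 140 or censoring at day 140. Neither choice gives day 84.

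**Example 2, PFS.** Agreed SD on day 84, unadjudicated disagreements on days 140 and 196, agreed PD on day 252. The gap is 252 − 84 = 168 days, above 126, so the agreed PD is censored at day 84. Had day 196 been kept as non-PD, the gap would be 252 − 196 = 56 days and the PD would count. This assumes that a dropped scan cannot serve as the last adequate scan; SAP 9.3 does not say.

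**Response.** The SAP 14.1 rules were applied to scans at weeks 6, 12, 20 and 28 in subjects with no adjudication:

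| Reader 1 | Reader 2 | Reader 1 alone | Reader 2 alone | After dropping |
|---|---|---|---|---|
| PR-PR-SD-PD | SD-PR-PR-PD | PR | PR | SD |
| PR-PR-PD | PR-SD-PD | PR | SD | SD |
| PR-PD-PR-PR | PR-SD-PR-PR | SD | PR | PR |

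In the first row both readers have a confirmed PR, but only the week-12 PR survives. In the third row the scan called PD by one reader disappears and the subject counts as a responder. The denominator is the whole analysis set, so with 90 subjects each change moves central cORR by 1/90 = 1.1 points. For scale, 37/90 = 41.1% (exact 95% CI 30.8 to 52.0) and 36/90 = 40.0% (29.8 to 50.9).

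**Illustration for the PFS median.** These inputs are assumptions, not figures for this trial:

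- exponential PFS with median 8.0 months (the earlier study's safety lead-in, cited in the protocol synopsis);
- cut-off 6 to 18 months after first dose;
- readers disagree on 20% to 40% of progression scans;
- 50% to 80% of the affected subjects have no later scan;
- the comparator counts every such progression as an event.

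The median is taken as ln 2 × person-time / events. With nothing dropped it is about 8.6 months, because progression is dated at the next scan.

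| Disagreements left open | Upward shift in central PFS median |
|---|---|
| 0% | 0% |
| 10% | 1% to 3% |
| 25% | 3% to 8% |
| 50% | 6% to 18% |
| 100% | 12% to 44% |

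An adjudicator would sometimes choose the non-PD reader, so the shift against true adjudicated results would be smaller.

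**The case against.** The strongest reply is that these are residual rules. The section says discrepancies are adjudicated; if that is done, 1b and 2b-ii never apply. The natural case is a reading still pending at a data cut, and the SAP says central results may change as later scans are reviewed, so a loss at Stage 2 could be reversed at a later analysis. This stands in part: full adjudication removes the problem. But the SAP writes the rule twice, gives no reason or limit, and Protocol 13.1 plans the study report at the primary analysis, so a Stage 2 loss could be reported.

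Three stronger readings are tempting and not supported:

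- **That every unadjudicated discordant scan is lost.** Rule 2a keeps one that precedes a later adjudication for the same subject.
- **That central cORR is biased downward.** It can move either way, and one dropped scan often changes nothing, because Table 10 still confirms PR-NE-PR.
- **That the trial's main conclusion is at risk.** The only confirmatory test is on local cORR (SAP 8). The 37-of-90 rule and its stated error rate and power do not use central readings. Central PFS is supportive, and no section names central cORR as the check on the primary result.

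It is also fair that the PFS sensitivity analysis (Table 13) counts the day-252 event in Example 2. It does not restore the scan in Example 1, and no equivalent is planned for DOR.

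**Conclusion.** The rule as written selects scans on the readings themselves and should be changed. Dropping a scan that one reader called PD cannot create a PFS or DOR end event; it can only delay or remove one, which favours the treatment. DOR can also be shortened if the first response scan is dropped. Central cORR can go up or down.

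The size is unknown because the documents give neither reader-discordance nor open-adjudication rates. It is zero if every discrepancy is adjudicated; the percentages above hold only under their assumptions. Secondary central endpoints are affected; the primary analysis is not. The point merits a change to the SAP but does not put the trial's main test in question.

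**What to change.** 1. Require every discordant time point up to the cut-off to be adjudicated before each snapshot.
2. Where one is still open after an earlier adjudication, replace 2b-ii by carrying forward the reader selected at that subject's last adjudication, as 2b-i already does for concordant scans. A never-adjudicated subject (1b) has no selected reader to carry, so step 1 is the remedy there.
3. Report the number of discordant scans still unadjudicated, and state how any scan still dropped counts under SAP 9.3.
4. Rerun central cORR, PFS and DOR with all reader-01 readings and with all reader-02 readings. Use the less favourable reading for open scans as a sensitivity analysis only; in the main analysis it could replace undercounted progressions with overcounted ones.

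Cost: SAP wording, a delivery condition for the imaging vendor, and a few extra tables. The adjudicator is already planned, so no new reader is needed, but the snapshot may wait for open adjudications.
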